15.1 Statistical considerations

The proportion of patients that did not require mechanical ventilation or die within 29 days of randomization will be recorded as a preliminary assessment of the efficacy of duvelisib in this setting.

Definition of subjects evaluable for efficacy response

Subjects who completed screening and enrollment procedure and who are randomized to receive duvelisib/placebo will be evaluable for efficacy endpoints on an intent-to-treat basis.

Definition of NIAID scale

The clinical response to study drug is defined as the first day on which the subject satisfies the criteria of a score of 5 or greater in the following categories from the NIAID ordinal scale. The NIAID ordinal scale is an assessment of the clinical status at the first assessment on a given study day. The scale is as follows: 1) Death; 2) Hospitalized, on invasive mechanical ventilation or extracorporeal membrane oxygenation (ECMO); 3) Hospitalized, on non-invasive ventilation or high flow oxygen devices; 4) Hospitalized, requiring supplemental oxygen; 5) Hospitalized, not requiring supplemental oxygen - requiring ongoing medical care (COVID-19 related or otherwise); 6) Hospitalized, not requiring supplemental oxygen - no longer requires ongoing medical care; 7) Not hospitalized, limitation on activities and/or requiring home oxygen; 8) Not hospitalized, no limitations on activities.

Definition of the primary efficacy endpoint

The proportion of patients who do not require mechanical ventilation (e.g. intubation, high-flow O₂ Bi-PAP or AIRVO) and who survive to 4 weeks after randomization will be used as the primary measure of efficacy.

Study design

This is a randomized placebo-controlled double blind/double masked phase 2 study to explore the efficacy of exposure to a PI3K inhibitor in patients with severe COVID-19. Subjects who are randomized to receive duvelisib or placebo will be evaluable for the primary and secondary efficacy analyses. All subjects with any exposure to duvelisib will be evaluable for toxicity (please see section 13.3 on grading of toxicities). A total of 80 subjects will be planned for analysis of the primary and secondary endpoints. We estimate that five subjects will be enrolled every month. One interim analysis is planned upon 50% (n=40) of subjects enrolled, which allows us the

Protocol Title: Duvelisib Ameliorates Manifestations of Pneumonia in Established Novel Coronavirus Infection (DAMPEN-CI)

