opportunity to stop the trial early due to futility or safety concerns. The only groups that will have access to unblinded interim data: (a) an independent data monitoring committee (IDMC); and (b) an independent statistical team whose role will be to generate the reports to be reviewed by the IDMC. The responsibility of any data-informed recommendations regarding continuing/stopping the study or modifying the study design/protocol be restricted to the IDMC.

Power Calculation

The reported incidence of death or mechanical intubation for patients with severe COVID-19 is approximately 40% (1). Local experience with COVID-19 patients at the Emory hospitals is consistent with this estimate, as 29% of all SARS-CoV-2 positive patients (n=800) are admitted to the ICU with COVID-19, and that 22% of all admitted patients are intubated, and 37% of intubated patients die in hospital. A favorable and clinically significant result from treatment with duvelisib in high-risk COVID-19 patients would be to reduce the composite incidence of death/mechanical ventilation from 40% to 15%. A sample size of 40 subjects for each treatment group will have >80% power to detect a 25% absolute reduction in the proportion of subjects who experience death or mechanical ventilation, comparing a predicted proportion of 40% death or intubation in the control arm to 15% death or intubation in the experimental arm receiving duvelisib treatment. The calculation is based on 10% type 1 error rate and two-sided Mantel-Haenszel test with one planned interim analysis when approximately 50% of sample enrolled (N=20/treatment). For

Analysis of Primary Endpoints

Analysis of the primary end-point will be based upon an intent-to-treat analysis of all subjects who are randomized to receive duvelisib/placebo. The primary endpoint is the proportion of patients who will require mechanical ventilation or experiencing death within 4-weeks (29 days) after randomization, which will be estimated with the corresponding 95% Clopper-Pearson confidence interval for the two arms separately. Fisher's Exact test will be used to test the difference between the two arms. In addition, a logistic regression will be used to estimate the odd ratio between the two arms controlling for the baseline covariates for an improved precision of the estimation (30).

Analysis of Secondary Endpoints

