Evaluable subjects will be all subjects who were randomized to receive duvelisib or placebo. The definition of secondary endpoints are listed in section 2. The descriptive statistics will mainly be applied to all secondary endpoints by treatment arms separately, such as frequency and percentage for categorical endpoints and mean, median, and standard deviation for numerical endpoints. They will be compared between treatment arms by Fisher's Exact test for categorical endpoints and Wilcoxon Rank-Sum test for numerical endpoints. For biomarkers measured repeated over time, generalized estimating equation (GEE) model will be used to test the difference in change pattern over time by two treatment groups using a nonlinear model. P-value will be adjusted for multiple comparison if necessary. Time to recovery is as the days from randomization to reach the desired NIAID ordinal scale ≥ 5 , a log-rank test will be used to compare the difference between the two arms. Survival rate at day 50 - 60 will be estimated by Kaplan-Meier method with log-rank test.

Interim Analysis for futility

The responsibility of any data-informed recommendations regarding continuing/stopping the study or modifying the study design/protocol be restricted to the independent data monitoring committee (IDMC), which is a part of the Winship data safety monitoring committee (DSMC). Upon 20 enrolled for each arm, an interim analysis will be carried out by two-sided Mantel-Haenszel test. O'Brien-Fleming boundary for futility is 2.373 on the Z score (equivalently: 0.991 on the fixed sample p-value scale). The trial may be terminated due to futility, or

Protocol Title: Duvelisib Ameliorates Manifestations of Pneumonia in Established Novel Coronavirus Infection (DAMPEN-CI)

following review by the IDMC of clinical and laboratory immune-monitoring data. Otherwise, the trial will continue enrolling patients until all 80 patients enrolled.

Stopping Rule for Safety

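### The >80% power belongs to an uncorrected Mantel-Haenszel test; the primary test actually named, Fisher's exact test, has about 75% at 40 per arm

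*Combined protocol and SAP*

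**What the plan says.** All the relevant text is in section 15.1 of the combined protocol and SAP.

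- **Power Calculation, sample size:** "A sample size of 40 subjects for each treatment group will have >80% power to detect a 25% absolute reduction". The rates assumed are 40% on control and 15% on duvelisib.
- **Power Calculation, test and level:** "The calculation is based on 10% type 1 error rate and two-sided Mantel-Haenszel test with one planned interim analysis".
- **Analysis of Primary Endpoints, between-arm test:** Fisher's "Exact test will be used to test the difference between the two arms". The sentence gives neither a significance level nor sidedness.
- **Analysis of Primary Endpoints, model:** "In addition, a logistic regression will be used to estimate the odd ratio between the two arms", adjusted for baseline covariates. Its stated purpose is estimation.
- **Interim Analysis for futility:** at 20 per arm, "an interim analysis will be carried out by two-sided Mantel-Haenszel test", with a boundary of 2.373 on the Z scale.
- **Opening of 15.1:** the primary proportion "will be recorded as a preliminary assessment of the efficacy of duvelisib in this setting".

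**The concern.** The test that was powered is not the test that will be run. Fisher's exact test conditions on the total number of events and is conservative at this sample size. A plan that budgets a 10% type I error and then uses Fisher's test spends well under 10%, and it pays for that in power. If the gap is material, the headline power statement is wrong for the primary analysis.

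The synopsis says the trial is to decide whether duvelisib merits a larger study, so a false negative is the costly error here. The section also has two between-arm tests on record for the same endpoint, one for power and the interim look and one for the final analysis, and they can give opposite answers. If that is not settled before unblinding, the choice could be made with the data in view.

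**Working it through.** **Inputs (15.1 unless noted).** n = 40 per arm, N = 80; 1:1 allocation (section 1.2); p1 = 0.40, p2 = 0.15; two-sided alpha 0.10, so z = 1.645. There is no dropout inflation, because patients who withdraw consent before the endpoint are replaced. *Assumption:* Fisher's test uses the same two-sided 0.10.

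**Step 1. Reproduce the plan's figure by normal approximation.** Power = Φ{[|p1 − p2|√n − z√(2p̄(1 − p̄))] / √(p1(1 − p1) + p2(1 − p2))}, with p̄ = 0.275.

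- |p1 − p2|√n = 0.25 × 6.325 = 1.581
- z√(2 × 0.275 × 0.725) = 1.645 × 0.6315 = 1.039
- √(0.24 + 0.1275) = 0.6062
- Power = Φ(0.542 / 0.6062) = Φ(0.895) = 81.5%

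The claim of more than 80% reproduces.

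**Step 2. Exact power of each test.** Take all 41 × 41 outcome pairs, weight each by its two binomial probabilities, and add the weights where the test rejects. The Mantel-Haenszel statistic for a single table with cells a, b, c, d is (N − 1)(ad − bc)² / (product of the four margins). The corrected version replaces |ad − bc| by |ad − bc| − N/2.

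| Test, two-sided 0.10, 40 per arm | Power at 40% vs 15% | Maximum true size |
|---|---|---|
| Mantel-Haenszel, uncorrected | 82.2% | 11.75% (common rate 6.75%) |
| Mantel-Haenszel, corrected | 74.5% | 6.0% |
| Fisher | 75.5% | 6.1% |
| Boschloo (Fisher p-value cutoff 0.154) | 81.6% | 9.7% |

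The loss from using Fisher's test is 82.2 − 75.5 = 6.7 points (6.8 before rounding). The miss rate is 100 − 75.5 = 24.5% against 100 − 82.2 = 17.8%.

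**Step 3. How often the conclusion changes.** Under 40% vs 15%, uncorrected Mantel-Haenszel and Fisher disagree in 6.8% of trials, and Fisher is always the non-significant one. Example: 14/40 vs 7/40.

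- ad − bc = 14 × 33 − 26 × 7 = 280
- Margins: 40 × 40 × 21 × 59 = 1,982,400
- Uncorrected: 79 × 280² / 1,982,400 = 3.124, p = 0.077
- Corrected: 79 × 240² / 1,982,400 = 2.295, p = 0.130
- Fisher: p = 0.126

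**Step 4. Sample size for Fisher.** Power is 79.8% at 45 per arm and 80.9% at 46 per arm, so 80% needs 46 per arm.

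**Step 5. Sensitivity.**

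- *Other 25-point reductions, from 35% vs 10% to 60% vs 35%:* Fisher is 5.9 to 8.2 points below uncorrected Mantel-Haenszel.
- *Interim look:* the documents give no final critical value. The stated 2.373 is √2 × 1.678, which is the two-look O'Brien-Fleming pattern, so 1.678 (two-sided 0.0933) is an assumed final value. Power is then 80.8% uncorrected, 73.7% corrected and 73.7% Fisher.
- *Fisher at two-sided 5%:* 64.1%, against 72.3% for uncorrected Mantel-Haenszel.

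**The case against.** The case for leaving the plan alone is reasonable in several respects. This is a phase 2 trial described as preliminary. Fisher's test is valid and conservative, and 15.1 also uses it for the categorical secondary and safety endpoints, so it is a coherent choice. Against the promised 80% the shortfall is about 4.5 points; the larger gap is measured against a computed 82.2% that the plan never states. All of that stands, and it limits the weight of the point. It does not make the power statement true of the named test.

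Four technical objections also deserve an answer.

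- **Level.** The sentence naming Fisher's test gives no alpha, so 75% is conditional on 10%. That is correct. At 5% the power is lower still.
- **Final critical value.** Testing at 1.645 at the end is safe only if the interim cannot stop for efficacy. If 2.373 were used that way, the overall size would be about 10.6% with 1.645 and 10.0% with 1.678 (normal approximation). Section 15.1 limits the interim to futility or safety, but section 8.2 lists demonstrated efficacy as a reason to terminate. The replacement wording must cover this.
- **Stratification.** Randomization is stratified by site, and Mantel-Haenszel is often run stratified. The plan does not say which form it means. The figures here are for a single table.
- **Incomplete text.** The power paragraph breaks off mid-sentence, so a clarification could have been lost. The two visible sentences still conflict.

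**Conclusion.** The point holds. The stated power is correct for an uncorrected, single-table Mantel-Haenszel test (82.2%). It is not correct for Fisher's exact test, the only between-arm test named for the primary endpoint, which has 75.5% power under the same inputs. The logistic regression does not close the gap, because it is there to estimate an odds ratio.

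The result assumes 40 analysed per arm and Fisher's test at two-sided 10%. Its direction holds across the other 25-point reductions examined, at the assumed O'Brien-Fleming final level and at 5%. This should be fixed, but it does not threaten the validity of the trial.

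**What to change.** Amend Analysis of Primary Endpoints in 15.1 before unblinding. State the alpha and choose one of the following.

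1. **Make Mantel-Haenszel primary.** Specify it without continuity correction, at two-sided 0.10, with Fisher's test as a sensitivity analysis, and say whether it is stratified by site. This matches the power calculation. If an efficacy stop at the interim is intended, use the final value 1.678 instead. The cost is that guaranteed size control is lost: the single-look exact size is 9.0% to 10.2% for common event rates of 15% to 50%, 10.9% at 10%, and 11.75% at its peak near 7%. The wording must exclude the continuity correction, because the corrected test has 74.5% power and does not support the claim either.
2. **Name Boschloo's unconditional exact test.** Power is 81.6% with a maximum size of 9.7%. The cost is that the final test differs from the interim Mantel-Haenszel test.
3. **Keep Fisher's test and restate its power as about 75%.** This is the least intrusive change and a legitimate choice where strict size control is wanted. The cost is accepting power below 80%, or planning 46 per arm to regain it.

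At 40 per arm, each option is a text change to 15.1 and needs no extra patients or data.

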Endpoints:	
Primary Endpoint:
 
1. Composite endpoint of either mechanical ventilation or death within 29 days of randomization 
Secondary Endpoints:
 
2. Days to recovery as assessed by ACTT endpoints as the time to recovery (Day 1 through Day 29) to satisfy one of the following eight categories from the NIAID ordinal scale. The scale is as follows: 1) Death; 2) Hospitalized, on invasive mechanical ventilation or extracorporeal membrane oxygenation (ECMO); 3) Hospitalized, on non-invasive ventilation or high flow oxygen devices; 4) Hospitalized, requiring supplemental oxygen; 5) Hospitalized, not requiring supplemental oxygen - requiring ongoing medical care (COVID-19 related or otherwise); 6) Hospitalized, not requiring supplemental oxygen - no longer requires ongoing medical care; 7) Not hospitalized, limitation on activities and/or requiring home oxygen; 8) Not hospitalized, no limitations on activities.3. Duration of hospitalization4. Duration of hospitalization5. Death within 29 days of randomization6. ICU transfer within 29 days of randomization7. ECOG performance status at day 15 and 29 of randomization8. Incidence of grade III-V adverse events or SAEs (as defined by CTCAE version 5)9. Documented secondary bacterial or viral infection within 29 days of randomization.10. Mean frequencies of Th1 and Th17 T cells in blood mononuclear cells at 1, 2 and 4 weeks11. Mean levels of inflammatory serum biomarkers at 1, 2 and 4 weeks12. Gene expression profiles of T cells at 1, 2 and 4 weeks13. Median titers of IgG antibodies to SARS-CoV-2 at 4 weeks
Study Population:	80 adults aged 18 years or older will be enrolled with severe, confirmed COVID-19
Phase:	Phase 2 randomized, placebo-controlled study
Description of Sites/Facilities Enrolling Participants:	This study will begin at Emory University and will seek to open at one or more secondary site institutions.

[figure not shown]

Protocol Title: Duvelisib Ameliorates Manifestations of Pneumonia in Established Novel Coronavirus Infection (DAMPEN-CI)

Description of Study Intervention:	Duvelisib is an oral PI3K inhibitor that is given at a dose of 25 mg BID
Study Duration:	We estimate that the duration of the study will be approximately 12 months. Participant duration will be approximately 1 month from the time of enrollment

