1.2 Schedule of Assessments

Following screening, informed consent, and confirmation that a patient with severe COVID-19 meets all eligibility criteria, subjects will be randomized 1:1 to receive duvelisib 25 mg, po BID or a placebo pill, po BID. Randomization between duvelisib 25 mg po BID and placebo BID will be stratified by study site. The investigational pharmacy will supply coded study drug based upon the results of central randomization.

Procedures and Tests Study Tests DURING HOSPITALIZATION [#]	Days -2 to 0 [@]	Day 1 [@]	Day 8 (± 2)	Day 15 (± 2)	Day 29 (± 3)	Day 50-60
Randomization to duvelisib or placebo arm	X					
Study Drug Administration		Oral drug BID Days 1-14				
SARS-CoV-2 RT-PCR	X					
Immunophenotyping of immune cells in blood		X	X	X	X	
Whole blood for RNA gene expression ^{##}		X	X	X	X	
Mononuclear cells for mass cytometry ^{##}		X	X	X	X	
Plasma cytokines and chemokines ^{##}		X	X	X	X	
Anti-SARS Cov-2 IgG		X			X	
TSH	X				X	
Hepatitis Serologies if known history of treated Hepatitis B or C	X					

Standard of Care Tests*	Days -2 to 0	Day 1	Day 8 (± 2)	Day 15 (± 2)	Day 29 (± 3)	Day 50-60
Physical Exam	X	Performed daily during hospitalization				
ECOG Performance Status	X	Performed daily during hospitalization				
Vital Signs	X	Performed daily during hospitalization				
Clinical Labs: Record data in eCRF (REDCap) during hospitalization as shown below						
CBC with differential	X	Abstract data as available				
CMP	X	Abstract data as available				
Ferritin		Abstract data as available				
CRP, Troponin		Abstract data as available				
Coagulation Tests**		Abstract data as available				
Non-contrast Chest CT or Chest X-Ray	X	Abstract data as available				
Serum or Urine Pregnancy Test***	X					
Assessment of Survival Status						X

study procedures which are performed as part of the research protocol and covered by the study budget

Additional research blood samples will be obtained prior to discharge from hospital

@ Some overlap of procedures and tests performed for screening and Day 1 is expected.

* Standard of care procedures which are routinely performed on COVID-19 patients and the results of which will be recorded as part of study conduct

** PT/INR, PTT, Fibrinogen, D-Dimer, Heparin/Enoxaparin Anti Xa

*** Pregnancy test for WOCBP may be obtained after hospital admission but prior to study enrollment

2. Objectives (and Endpoints)

OBJECTIVES	ENDPOINTS
Primary	

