Summary statistics and frequencies for the following characteristics will be described by randomized arms: ECOG, Race, Ethnicity, Age, Sex, Body mass index (BMI), Medical history of hypertension, diabetes, asthma, chronic obstructive pulmonary disease, History of and treatment for cancer, History of coronary artery disease (prior MI, CABG, coronary artery stent, or medical management), History of prior pulmonary infections (TB, pneumonia, influenza), Allergies

Subgroup analyses

None

15.2 Data/specimens:

Source Documents

Source data is all information, original records of clinical findings, observations, or other activities in a clinical trial necessary for the reconstruction and evaluation of the trial. Examples include medical records (hospital records, office charts), laboratory results, imaging scans and reports, EKGs, patient diaries, videos, photographs, pharmacy dispensing, and other records, investigator or patient completed questionnaires involved in the clinical trial.

Case Report Forms

The case report form (CRF) will be the primary data collection instrument for the study. All data requested on the CRF will be recorded and all entries will be recorded into an electronic data capture system by authorized personnel. The principal investigator is responsible for assuring that the data entered into the CRF are complete, accurate and that entries are updated in a timely fashion. Data will be entered in the clinical research data management system – REDCap - per Winship SOP 4.2 Data Completion Metrics. REDCap will be used to record all study related information and data for all registered subjects, including their assigned patient ID. All data submitted must be accompanied by supporting source documents, where applicable and as outlined in the protocol-specific monitoring plan. Data completion will be reviewed monthly. In situations where there are significant delays of data completion, the Associate Director of Clinical Research or the Director of Clinical Trials may temporarily suspend enrollment. All data must be entered in the timeframe required at each site, but no later than 30 days following registration and each visit completion. All queries are to be resolved within 4 weeks of issue. The coordinating center multi-site coordinator will provide REDCap training and request access to the appropriate staff at the participating site.

Procedures to Ensure Capturing Data for the Primary End-point

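### Randomisation is stratified by site but no stated test is; if sites differ, the comparisons become conservative and lose some power

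*Combined protocol and SAP*

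**What the plan says.** Section 1.2 (Schedule of Assessments) sets the allocation: "subjects will be randomized 1:1 to receive duvelisib 25 mg, po BID or a placebo pill, po BID". It goes on: "Randomization between duvelisib 25 mg po BID and placebo BID will be stratified by study site". Section 11 repeats this, and no other stratification factor is given. On the number of sites, the synopsis says: "This study will begin at Emory University and will seek to open at one or more secondary site institutions".

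Section 15.1 sizes the trial as follows: "A sample size of 40 subjects for each treatment group will have >80% power to detect a 25% absolute reduction", from 40% to 15%. On the method it adds: "The calculation is based on 10% type 1 error rate and two-sided Mantel-Haenszel test with one planned interim analysis". The interim analysis is also a Mantel-Haenszel test. No strata are named in either place.

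For the final primary analysis, Fisher's "Exact test will be used to test the difference between the two arms". A supporting logistic regression adjusts for baseline covariates that are not listed. Secondary endpoints are compared by Fisher's test (categorical), the Wilcoxon rank-sum test (numerical) and GEE (repeated biomarkers). For time to recovery, "a log-rank test will be used to compare the difference between the two arms"; survival at day 50-60 also has a log-rank test. None of these is described as stratified by, or adjusted for, site.

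**The concern.** Stratified allocation makes the arms alike within each site. If sites differ in outcome, that between-site variation no longer contributes to chance differences between the arms. A test that pools over site still counts it as noise. Its standard error is then too large, its true level falls below nominal, and some of the benefit of stratifying is lost.

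Site differences are plausible here. In section 15.1 the primary endpoint counts high-flow oxygen, Bi-PAP and AIRVO as well as intubation, and escalation to these depends on local practice. Section 5.4 leaves standard of care to local decision. Section 5.6 has clinical laboratory samples analysed at Emory or secondary-site laboratories.

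At stake is efficiency in an 80-patient trial, and agreement between the design and the analysis.

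**Working it through.** **Inputs from the plan.** 40 per arm; 40% against 15%; two-sided 10%; one interim look; O'Brien-Fleming value 2.373 at half the sample; allocation 1:1 within site.

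**Inputs assumed, because the plan gives none.** The number and size of sites, and how their rates differ. The main case is two equal sites with the overall control rate held at 40%. A common odds ratio across sites is set so that the overall duvelisib rate is 15%.

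**Step 1: the plan's own figure.** Pooled rate = (0.40 + 0.15)/2 = 0.275.

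- SE under the null = √(2 × 0.275 × 0.725/40) = 0.0998.
- SE under the alternative = √((0.40 × 0.60 + 0.15 × 0.85)/40) = 0.0959.
- Fixed-sample power = Φ((0.25 − 1.645 × 0.0998)/0.0959) = 81.5%.
- A two-look, two-sided O'Brien-Fleming design at 10% has bounds 2.373 and 1.678. The first matches the plan. Using 1.678 at the final look gives 80.5%.

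The stated power above 80% reproduces for an unstratified Mantel-Haenszel test.

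**Step 2: why pooling is conservative.** The ratio of the true to the assumed null variance is R = mean of p(1 − p) within sites ÷ p(1 − p) at the overall rate. The approximate level of the unstratified test is 2[1 − Φ(1.645/√R)].

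- Control rates 30% and 50%: R = [(0.21 + 0.25)/2]/0.24 = 0.958; level about 9.3%.
- Control rates 20% and 60%: R = [(0.16 + 0.24)/2]/0.24 = 0.833; level about 7.2%.

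Actual levels are somewhat lower because the data are discrete.

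**Step 3: same statistic, with and without strata.** These are simulated, uncorrected, fixed-sample results at two-sided 10%. Repeat simulations and an exact enumeration of the two-site tables agree to within about 0.4 points.

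| Control rates by site | Power, unstratified | Power, stratified | Gain (points) | Level, unstratified | Level, stratified |
|---|---|---|---|---|---|
| 40% / 40% | 82.1% | 82.3% | 0.2 | 9.1% | 9.3% |
| 30% / 50% | 82.8% | 83.5% | 0.7 | 8.3% | 9.6% |
| 20% / 60% | 83.6% | 86.1% | 2.5 | 6.2% | 10.2% |
| 10% / 70% | 85.9% | 91.1% | 5.2 | 3.2% | 9.9% |

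With a 10-point gap (35% / 45%), power is 82.4% against 82.7%. With sites split 75:25 and a 20-point gap (35% / 55%), it is 82.6% against 83.3%.

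**Step 4: the test actually named.** Fisher's test has level 5.6% and power 75.5% with no site difference at all. At 30% / 50% its level is 5.1%, and at 20% / 60% it is 3.5%. The move from Mantel-Haenszel to Fisher costs about 7 points of power (82.2% − 75.5% = 6.7), more than any plausible site effect.

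**Step 5: numerical endpoints.** Assume a 0.5 SD treatment effect. With no site shift, Wilcoxon and the site-stratified van Elteren test both have about 69% power. With sites 1 SD apart, it is about 62-65% against 69-70%. With sites 1.5 SD apart, it is about 52-56% against 69-70%. No shift of this size is documented.

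**The case against.** Only one site is certain; section 10 calls the others potential. With one site, stratifying changes nothing. At site gaps of 10 to 20 points the loss is 0.3 to 0.7 points of power, and the larger figures need gaps that the documents do not suggest. This stands, and it limits the size of the point.

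Four stronger readings are tempting, and the documents do not support them.

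- **Site is excluded from every analysis.** The Mantel-Haenszel strata and the logistic covariates are unspecified, so site is unnamed but not ruled out.
- **Ignoring site takes the trial below its planned power.** In every scenario above, the unstratified Mantel-Haenszel test stays above 80%. The drop to about 75% comes from Fisher's own conservatism.
- **Secondary comparisons miss a stated error level.** Section 15.1 states no level for them, so only the primary comparison can be judged against one.
- **The logistic model is overloaded by the baseline table.** That table is descriptive: "Summary statistics and frequencies for the following characteristics will be described by randomized arms". Nothing makes it the model's covariate list.

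The Wilcoxon figures also do not carry over to the GEE, which tests change over time; a constant site offset largely cancels there. T-cell phenotyping is done centrally at Emory (section 15.2), which reduces laboratory differences for those endpoints.

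**Conclusion.** The point holds as a modest improvement at almost no cost. Site is the only stratification factor, and no stated test uses it. If a second site enrols enough patients and sites differ, the primary comparison gives up about 0.7 points of power at a 20-point difference in control rates and about 2.5 points at a 40-point difference. Its true level falls to 8.3% and 6.2% respectively, for an uncorrected statistic at nominal 10%. These sizes rest on two equal sites, a common odds ratio, fixed-sample testing and assumed site rates. Losses on numerical endpoints could be larger, but only with site shifts of 1 SD or more. A reader might infer that the planned analysis is invalid. It is not: the error is on the conservative side.

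**What to change.** In section 15.1:

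1. Make the primary test a Cochran-Mantel-Haenszel test stratified by randomisation site, and name the same strata for the interim test. This is the family already used for sizing. State that no continuity correction is used; with one, power is 74.7% when sites do not differ.
2. Set in advance a rule for pooling small sites, and say that the test reduces to the unstratified form if only one site enrols.
3. Use site-stratified log-rank tests for time to recovery and survival, and van Elteren's test for numerical endpoints.
4. Include site in the GEE and logistic models.

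The cost is wording and the pooling rule. No patient procedure changes. If sites do not differ, the primary test loses nothing and numerical endpoints may lose up to about 1 point of power. The stratified test is asymptotic, and its level reached 10.2% in one scenario.
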